9.2.2 Version 3 Changes

The SAP was updated to reflect changes in protocol amendment 6. Changes from version 2 are summarized below:

- Sec 5.3: updated the definition of ‘efficacy-evaluable set’ to allow adequate follow up for response related endpoints at the time of interim analyses

- Sec 6.2 and 6.10: clarified the timing of Cohort 2 analyses and added additional interim analysis for Cohort 2 after approximately 70 subjects have been followed for approximately 8 months from the first dose of study drug

9.2.3 Version 4 Changes

Changes from version 3 are summarized below:

- Corrected section numbering for 6.4.3, 6.4.4, and 6.4.5
- Sec 6.8: clarified the number of subjects required in a subgroup to enable the subgroup analysis
- Sec 10: removed the references that were not cited in the SAP
- Appendix B: added additional details to the TEAE definition to account for changes in seriousness or relatedness for events that continue from the baseline conditions

APPENDIX A: IMPUTATION OF PARTIAL MISSING ADVERSE EVENT DATES

The algorithm below should be used to impute pre-existing condition and adverse event (AE) start dates for which only partial information is known. For ease of reading, both pre-existing conditions and AEs will be referred to as AE for the remainder of this document. The algorithm should be applied to every AE record on a record by record basis. AE start dates should be imputed before imputation of AE condition end date in all cases. The AE condition end date should only be used in the imputation of the AE start date if it is a complete, known date.

AE day and month are missing

- If the year is the same as the year of first dose of study treatment and the onset period and/or onset time indicate that the start of the AE was pre-dose:
 - AE start date will be imputed as the minimum of (AE condition end date*, day prior to first dose of study treatment)
- If the year is the same as the year of first dose of study treatment and the onset period and/or onset time indicate that the start of the AE was post-dose:
 - AE start date will be imputed as the minimum of (AE condition end date*, first dose date of study treatment)
- If the year is before the year of first dose of study treatment:
 - AE start date will be imputed as the minimum of (AE condition end date*, December 31st see example 2 below)
- If the year is after the year of first dose of study treatment:
 - AE start date will be imputed as the minimum of (AE condition end date*, January 31st see example 2 below)

AE month only is missing

- Treat day as missing and replace both month and day according to the above procedure

AE day only is missing

- If the month/year is the same as the month/year of first dose of study treatment and the onset period and/or onset time indicate that the start of the AE was pre-dose:
 - AE start date will be imputed as the minimum of (AE condition end date*, day prior to first dose of study treatment)
- If the month/year is the same as the month/year of first dose of study treatment and the onset period and/or onset time indicate that the start of the AE was post-dose:
 - AE start date will be imputed as the minimum of (AE condition end date*, first dose date of study treatment)
- If the month/year is before the month/year of first dose of study treatment:

- AE start date will be imputed as the minimum of (AE condition end date*, last day of the month)
- If the month/year is after the month/year of first dose of study treatment:
 - AE start date will be imputed as the minimum of (AE condition end date*, last day of the month)

* Only use condition end date if known and complete end date is available.

The following algorithm should be used to impute AE condition end dates. The AE records for a condition/event should be sorted by the imputed start dates then record position (order of entry into the eCRF). After sorting, if any condition end date month/year is greater than any subsequent record end date month/year, then change the imputed start day only to end of month. Repeat as necessary.

After sorting the AE records, apply the following rules to partial or missing AE condition end dates:

For all records excluding the last chronological record for a condition/event

- AE condition end date will be imputed as the start date of the subsequent record

For the last chronological record for a condition/event

- If outcome is “recovered/resolved”, “recovered/resolved with sequelae”, or “fatal” apply the following:
 - If only year is provided for the end date and year is equal to the year of the last dose date:
 - AE condition end date will be imputed as the minimum of (last dose date+30, death date, data extraction date, December 31st of the end date year)
 - If only year is provided for the end date and year is not equal to the year of the last dose date:
 - AE condition end date will be imputed as the minimum of (death date, data extraction date, December 31st of the end date year)
 - If month and year are provided for the end date:
 - AE condition end date will be imputed as the minimum of (death date, data extraction date, last day of the end date month/year)
- If outcome is “recovering/resolving”, “not recovered/resolved”, “unknown”, or blank:
 - AE condition end date will not be imputed.

Example 1

AESPID 1: Condition/Event HEADACHE

First dose date 01JAN2012

Prior to imputation

Start date	Condition end date	Severity	Outcome	Onset
UNUNK2011	15APR2012	1	not recovered/resolved	pre-ICF
15APR2012	UNMAY2012	2	recovering/resolving	post 1st dose
UNMAY2012	UNJUN2012	1	not recovered/resolved	post 1st dose
UNJUN2012	UNJUN2012	3	recovering/resolving	post 1st dose
UNJUN2012	10JUL2012	2	recovering/resolving	post 1st dose
10JUL2012	--	1	not recovered/resolved	post 1st dose

Post imputation

Start date	Condition end date	Severity	Outcome
31DEC2011	15APR2012	1	not recovered/resolved
15APR2012	31MAY2012	2	recovering/resolving
31MAY2012	30JUN2012	1	not recovered/resolved
30JUN2012	30JUN2012	3	recovering/resolving
30JUN2012	10JUL2012	2	recovering/resolving
10JUL2012	--	1	not recovered/resolved

Example 2 (highlights choice of last day of the month as opposed to the 1st or the 15th)

AESPID 4: Condition/Event NAUSEA

First dose date 01APR2012

Prior to imputation

Start date	Condition end date	Severity	Outcome	Onset
UNUNK2011	25APR2012	1	not recovered/resolved	pre-ICF
25APR2012	UNAPR2012	2	recovering/resolving	post 1st dose
UNAPR2012	04MAY2012	1	recovered/resolved	post 1st dose

Post imputation

Start date	Condition end date	Severity	Outcome
31DEC2011	25APR2012	1	not recovered/resolved
25APR2012	31APR2012	2	recovering/resolving
31APR2012	04MAY2012	1	recovered/resolved

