7.6.1.1 Adverse Events of Special Interest

Peripheral neuropathy, corneal events, hyperglycemia, dermatological reactions, and infusion related reactions (IRR) are considered adverse events of special interest (AESI) for enfortumab vedotin. These are medical concepts of composite terms based on the search criteria (standard MedDRA query [SMQ] or sponsor specified query [SSQ]). Other AEs may be added to AESI as necessary. The search criteria for AESI will be maintained in a separate document and finalized prior to final database lock.

Treatment-emergent AESI will be summarized by PT and maximum severity. In addition, serious AESI, treatment-emergent AESI that are related to study drug, leading to dose modification and study treatment discontinuation will be summarized.

For selected AESI, time to onset, improvement, or resolution will be analyzed as appropriate.

Time to onset of a specific AESI will be calculated as time from the first dose of study drug to the start of first treatment-emergent event that meets the respective search criteria. In the analysis of time to onset of AE of a specific grade (e.g., grade 3 or higher), episode of events that are improved from a previous higher grade will not be included.

Resolution is defined as event outcome of ‘recovered/resolved’ or ‘recovered/resolved with sequelae’, or returning to baseline grade as of the latest assessment for conditions that are ongoing at baseline. For events with an outcome of ‘recovered/resolved’ or ‘recovered/resolved with sequelae’, time to resolution will be calculated as time from the event start date to end date. For events that return to baseline grade, time to resolution will be calculated as time from the start of treatment-emergent event to the date the event was last assessed.

For events that are not resolved, improvement is defined as decrease by at least one grade from the worst grade as of the latest assessment. For events that meet the definition of ‘improvement’, time to improvement will be calculated as time from the worst grade of the event to the date the event was last assessed.

Time to onset will be summarized at the subject level. Time to resolution and improvement will be summarized at the event level.

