 - b. For all baseline AEs, assign TEAE flag to 'N'
 - c. For post-baseline AEs where onset date is ≤ 30 days after last dose of study drug:
 - If the post-baseline AE is a continuing event of a baseline AE (i.e., events with the same AE identifier, where AE identifier is the number before the colon in SDTM AE.AESPID), then compare the CTCAE grade of the post-baseline AE to the CTCAE grade of the most recent baseline AE with the same AE identifier:
 - If the post-baseline AE has a higher CTCAE grade, then assign TEAE flag to 'Y'. All subsequent episodes of the same AE should have TEAE flag = 'Y' regardless of the CTCAE grade. If the CTCAE grade of the baseline AE is missing, then assign TEAE flag to 'Y'.
 - Else if the relationship to study drug changes from 'unrelated' to 'related' post-baseline, then assign TEAE flag to 'Y'.
 - Else if the seriousness of the AE changes from 'No' to 'Yes' post-baseline, then assign TEAE flag to 'Y'.
 - Otherwise, assign TEAE flag to 'N'
 - If the post-baseline AE is not a continuing event of a baseline AE, then assign TEAE flag to 'Y'

NOTE:

- **For summaries which include only treatment emergent AEs include all AEs which are classified as TEAEs as well as those AEs for which TEAE status could not be determined (e.g., the value of the TEAE variable may be missing if the event cannot be identified as baseline or post-baseline - missing information on the AE CRF should be queried). Only exclude those AEs which were determined to not be treatment emergent.**

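### SAP Appendix A sorts an event's grade-change records by imputed start date, so records with partial dates in the same month can be reversed without detection

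*SAP*

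**What the plan says.** All rules below are in SAP Appendix A unless another section is named.

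- **Start date, day missing, post-dose onset in the first-dose month:** "AE start date will be imputed as the minimum of (AE condition end date*, first dose date of study treatment".
- **Start date, day missing, later month:** "AE start date will be imputed as the minimum of (AE condition end date*, last day of the month". A footnote limits the use of the end date: "Only use condition end date if known and complete end date is available".
- **Sort:** "The AE records for a condition/event should be sorted by the imputed start dates then record position (order of entry into the eCRF".
- **Repair step, once the records are in order:** "if any condition end date month/year is greater than any subsequent record end date month/year, then change the imputed start day only to end" (that is, to the month's last day). The step is iterated as needed. The text does not say how a missing end date ranks in this comparison. It also does not say whether only the offending record's imputed start moves, or all of them.
- **End dates:** for every record but the last, if the end is partial or missing, "AE condition end date will be imputed as the start date of the subsequent record". A last record that is recovering, not recovered or of unknown outcome is left open.

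The results are used in three places. SAP 6.5 imputes AE dates for event duration and treatment-emergent status. Appendix B carries the flag forward once an event has worsened above its baseline grade: "All subsequent episodes of the same AE should have TEAE flag = 'Y' regardless of the CTCAE grade". SAP 7.6.1.1 applies to events not resolved: "improvement is defined as decrease by at least one grade from the worst grade as of the latest assessment". It defines resolution by event outcome or return to baseline grade, and summarises both at event level.

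**The concern.** In both worked examples each grade change is a separate record under one event. The order of these records decides which one is last, which end dates are filled in, and which records count as subsequent episodes. Appendix A takes that order from dates it has itself imputed: the first-dose date in the first-dose month, month-end afterwards. Either default can fall on the wrong side of a neighbouring record whose date is known. The only safeguard cannot see a reversal when the end dates share a month. A truly ongoing record that is no longer sorted last is then closed, and an earlier, superseded record can be left open.

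**Working it through.** I coded the rules literally and ran them under six readings of the repair step: a missing end date ranked lowest, ranked highest or skipped, each with either the offending record's or all imputed starts moved. Durations use End − Start + 1 (SAP 6.4.1).

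**1. The SAP's own examples.** Example 1 reproduces exactly. In Example 2 (first dose 01APR2012):
- Record 3 (Grade 1, UNAPR2012 to 04MAY2012, recovered) starts at min(04MAY2012, 01APR2012) = 01APR2012.
- It sorts ahead of record 2 (Grade 2, 25APR2012 to UNAPR2012).
- Its end month, May, is later than record 2's, April. The repair therefore fires, moves it to 30APR2012 and restores the order.

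The printed 31APR2012 is not a real date; month-end is 30APR2012. The example comes out right only because record 3 ends in a later month.

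**2. Example 2 with record 3 ending 28APR2012.** Its start is min(28APR2012, 01APR2012) = 01APR2012. All end months are April, so no repair fires. Result in 6 of 6 readings:

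| Sorted | Record | Grade | Start | End | Outcome |
|---|---|---|---|---|---|
| 1st | 1 | 1 | 31DEC2011 | 25APR2012 | not recovered |
| 2nd | 3 | 1 | 01APR2012 | 28APR2012 | recovered |
| 3rd | 2 | 2 | 25APR2012 | open | recovering |

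- The recovered Grade 1 record lasts 28 − 1 + 1 = 28 days. It cannot have begun before the Grade 2 record, so the most it could last is 28 − 25 + 1 = 4 days.
- The Grade 2 record, which ended by 28 April, has no end date.
- In true order, record 3 follows a worsening from Grade 1 to Grade 2 and is flagged Y by carry-forward. Reversed, it is Grade 1 against baseline Grade 1 and is flagged N, unless relatedness or seriousness changed.

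**3. A later month, with each end date chained to the next start as in the SAP examples.** First dose 01JAN2012.

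| Record | Grade | Recorded start | Recorded end | Imputed start |
|---|---|---|---|---|
| 1 | 1 | UNJUN2012 | UNJUN2012 | 30JUN2012 |
| 2 | 2 | UNJUN2012 | 20JUN2012 | min(20JUN, 30JUN) = 20JUN2012 |
| 3 | 3 | 20JUN2012 | ongoing | 20JUN2012 (known) |

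Record 1 sorts after record 3. In 6 of 6 readings the ongoing Grade 3 is closed at 30JUN2012, giving 30 − 20 + 1 = 11 days. The last record is Grade 1 or Grade 2, depending on the reading.

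**4. Two cases that hold only conditionally.**
- First-dose month, first dose 01APR2012: Grade 1 10APR2012 to UNAPR2012, then Grade 3 UNAPR2012, ongoing. Reversed in 4 of 6 readings. If a missing end ranks as latest, the repair moves Grade 3 to 30APR2012 and the order is right.
- Two records in May: Grade 1 UNMAY2012 to UNMAY2012, then Grade 2 12MAY2012 to 20MAY2012, recovered. Reversed in 6 of 6, but the end date is not chained to the next start. Chained, record 1 ends 12MAY2012, its start is min(12MAY, 31MAY) = 12MAY2012, and entry order breaks the tie correctly.

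**The case against.** The strongest defence has four parts.

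- **The repair step works in many cases.** It corrects reversals when end dates fall in different months and the misplaced start was imputed. It can also rescue a first-dose-month Grade 3 record if an ongoing event is ranked as ending last. This stands. A reader might infer that any such Grade 3 record is necessarily misordered; the documents do not support that, because the ranking is unstated. Steps 2 and 3 of the working do not depend on it.
- **The AESI consequence is an inference.** SAP 7.6.1.1 does not say that the latest assessment or the event outcome is read from the last sorted record. This stands. It is a natural reading of the appendix's term for the last record, but a programmer could do otherwise. In step 2 the recovered record keeps its complete end date.
- **Exposure is probably small.** The pattern needs partial dates and at least two records of one event starting in the same month. Protocol 7.7.1.2 asks for onset and resolution dates, and SAP Appendix B says missing AE form data should be queried. This stands, and is why the point is minor.
- **Entry order may not be chronological.** True, so contradictions should be queried. The SAP already relies on entry order as its tie-break.

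A reader might also link the first-dose rule to the protocol's remark that severe skin reactions occur mostly in the first cycle (5.4.3). That remark concerns 15 post-marketing patients, and the rule covers a calendar month, not a 28-day cycle. The link is too loose to use.

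**Conclusion.** The rule is wrong as written; the point is minor. Within one month, Appendix A can reverse an event's records with nothing to catch it, in a one-date change to the SAP's own Example 2 and in a fully chained June event, under all six readings of the repair step.

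Wrong end dates and durations follow directly. A wrong record-level TEAE flag follows in the Example 2 variant if subsequent episodes are taken in sorted order. False improvement of an ongoing Grade 3, or a resolved event shown as unresolved, follows in the descriptive AESI summaries only if those summaries read the last sorted record.

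A wider effect on the safety tables or on efficacy might be inferred, but is not supported. In the Example 2 variant the Grade 2 record is treatment-emergent in either order and a subject counts once at the highest severity, so incidence by maximum grade does not change. ORR uses none of these dates. The share of AE records affected is not given in the documents and is not estimated here.

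**What to change.** Amend SAP Appendix A as follows.

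1. Within an AE identifier, sort by the known year and month of the start date, then by eCRF record position. A record with only the year known keeps its entry position within that year. Query any record whose complete dates contradict the order.
2. Bound each imputed start. It may not fall before the previous record's start or complete end, nor before first dose if post-dose. It may not fall after its own complete end or the first complete date on any later record; looking only at the next record is not enough in the June case, where that record's start is itself partial.
3. Use the first-dose or month-end default only inside those bounds. If the first-dose default falls too early, use month-end, capped at the upper bound.
4. Replace the month/year repair step with these rules, and treat a missing end on an ongoing record as later than any known end date.
5. Correct 31APR2012 to 30APR2012 in Example 2.
6. State in SAP 7.6.1.1 which record supplies the latest grade and the outcome.

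Run on the same data, rules 1 to 3 reproduce Example 1, and Example 2 with 30APR2012. The April variant becomes Grade 2 from 25 to 28 April, then Grade 1 on 28 April, recovered. In the June event Grade 3 is last and open.

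The cost is a wording change, a change to the date-derivation program, reliance on entry order, and a few extra data queries. No new assessments are needed.

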APPENDIX B: DEFINITION OF THE TERM “TREATMENT-EMERGENT” WITH RESPECT TO AE CLASSIFICATION

The algorithm below should be used to determine whether an adverse event (AE) is classified as a treatment-emergent adverse event (TEAE). A TEAE is defined as any AE which is newly occurring or worsening in severity, where newly occurring means that the AE was not present at baseline. For ease of reading, both pre-existing conditions and AEs will be referred to as AEs for the remainder of this document. AE dates should be imputed in accordance with the algorithm detailed in [Appendix A](#) prior to determination of TEAE classification. Details of the TEAE classification are as follows:

- For each subject, determine the first dose date, which is the earliest date the subject receives any amount of study drug.
- **Baseline AEs:** classify an AE record as baseline AE if it satisfies both criteria a and b below:
 - a AE onset satisfies either of i, ii or iii below:
 - i. Onset date is prior to the first dose date
 - ii. Onset date is the same as the first dose date, and Onset Period is “started after consent but before the first dose of any study treatment” or Onset Time Relative to Study Treatment is “started before first infusion or before infusion on any dosing day”
 - iii. Onset Period is “started before the signing of consent” or “started after consent but before the first dose of any study treatment”
 - b AE end date satisfies either of i or ii below:
 - i. End date is the same as or after the first dose date
 - ii. End date is missing with outcome equal to
 - recovering/resolving, or
 - not recovered/not resolved, or
 - unknown or missing
- **Post-baseline AEs:** classify an AE record as post-baseline AE if it meets either of criteria a, b or c below:
 - a Onset date is after the first dose date
 - b Onset date is the same as the first dose date, and Onset Period is “started after the first dose of any study treatment” or Onset Time Relative to Study Treatment is not “started before first infusion or before infusion on any dosing day”
 - c Onset Period is “started after the first dose of any study treatment”

Note: at interim timepoint, if an AE is classified as both ‘baseline AE’ and ‘post-baseline AE’ due to data issues, the AE is to be considered ‘post-baseline AE’ in the derivation of TEAE flag.

- **TEAE flag** will be derived as follows:
 - a. For all AE records that have an end date prior to the first dose date, assign TEAE flag to 'N'
 - b. For all baseline AEs, assign TEAE flag to 'N'
 - c. For post-baseline AEs where onset date is ≤ 30 days after last dose of study drug:
 - If the post-baseline AE is a continuing event of a baseline AE (i.e., events with the same AE identifier, where AE identifier is the number before the colon in SDTM AE.AESPID), then compare the CTCAE grade of the post-baseline AE to the CTCAE grade of the most recent baseline AE with the same AE identifier:
 - If the post-baseline AE has a higher CTCAE grade, then assign TEAE flag to 'Y'. All subsequent episodes of the same AE should have TEAE flag = 'Y' regardless of the CTCAE grade. If the CTCAE grade of the baseline AE is missing, then assign TEAE flag to 'Y'.
 - Else if the relationship to study drug changes from 'unrelated' to 'related' post-baseline, then assign TEAE flag to 'Y'.
 - Else if the seriousness of the AE changes from 'No' to 'Yes' post-baseline, then assign TEAE flag to 'Y'.
 - Otherwise, assign TEAE flag to 'N'
 - If the post-baseline AE is not a continuing event of a baseline AE, then assign TEAE flag to 'Y'

NOTE:

- **For summaries which include only treatment emergent AEs include all AEs which are classified as TEAEs as well as those AEs for which TEAE status could not be determined (e.g., the value of the TEAE variable may be missing if the event cannot be identified as baseline or post-baseline - missing information on the AE CRF should be queried). Only exclude those AEs which were determined to not be treatment emergent.**

